9.3 Statistical Analysis Plan

The primary and some secondary analyses will include all eligible and treated patients. Exceptions to this include: analysis of toxicity data, which will include all patients who received study drug regardless of eligibility, and analyses of response, which will include eligible and treated patients with measurable and evaluable disease.

Time-to-event data, such as PFS and OS, will be estimated using the Kaplan-Meier method, and Cox proportional hazards models will be used to estimate the treatment hazard ratios. The primary comparison of PFS will use a logrank test stratified on the randomization stratification factors with a one-sided type I error rate of 10%. Other comparisons of groups will be made using the logrank test and Cox modeling.

Categorical data, such as response rates (CR+PR) and toxicity, will be compared using Fisher's exact tests with a one-sided type I error rate of 10%; multivariable logistic regression modeling will be used to adjust for the effect of any covariates that are associated with these categorical outcomes. Though none are currently planned, any continuous outcomes will be analyzed using Wilcoxon rank sum test, and multivariable linear regression models may be used to adjust for multiple associations with outcome.

Modeling procedures will implement backward selection; variables significant at the 0.10 level in the univariate setting will be chosen for inclusion in an initial full model, and at each step the least significant variable will be removed from the model. Only those covariates with $p < 0.05$ will remain in any final models, unless there are factors identified by the study team as crucial to model interpretation.

Point estimates of all endpoints will be accompanied by the corresponding two-sided 80% confidence intervals.

In the event that there are missing data, no imputation of the missing data will be conducted. We will assume that data are missing at random and will conduct all analyses as originally planned because we do not anticipate an excess of missing data.

Subset analyses are planned for all stratification factors and all known prognostic factors, such as performance status, age, sites of metastases, gender, etc. Subset analyses of all variables, including correlatives, are considered to be exploratory in nature.

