The current FDA approved dose of nivolumab is 240 mg IV every 2 weeks (recently changed from 3 mg/kg IV every 2 weeks). However, an alternative dosing strategy of 480 mg IV every 4 weeks is being pursued for approval as well. In anticipation of this, we will plan to administer nivolumab at the every 4 week schedule on this trial.

Activity of Nivolumab in NSCLC

Nivolumab, a monoclonal anti-PD-1 immunotherapeutic checkpoint inhibitor, is FDA approved for the treatment of squamous and non-squamous NSCLC. Of the second line treatment options currently available, immunotherapies more often result in prolonged benefit for a population of patients, with about 20% of patients having >12 month PFS. There is excitement about this new platform of therapy, but there is an unmet need to find drugs which synergize immunologically to allow a larger proportion of patients to benefit long term from therapy.

Nivolumab is also active in the second line treatment of non-squamous NSCLC, as demonstrated in the trial Phase III, Randomized Trial (CheckMate 057) of Nivolumab versus Docetaxel in Advanced Non-squamous (non-SQ) Cell Non-small Cell Lung Cancer (NSCLC) “[8] In this trial, nivolumab had an overall survival benefit compared with docetaxel.

	Nivolumab (n = 292)	Docetaxel (n = 290)
mOS, mo	12.2	9.4
	HR = 0.73 (96% CI: 0.59, 0.89); P = 0.0015	
mPFS, mo	2.3	4.2
	HR = 0.92 (95% CI: 0.77, 1.11); P = 0.3932	

The question of whether positive PD-L1 testing is necessary to predict benefit is currently an area of active investigation. With FDA approval of nivolumab, an optional “complementary diagnostic” of PD-L1 testing was also released. This diagnostic may help predict the likelihood of response, but is not required for treatment.

Activity of Nivolumab and Ipilimumab in NSCLC

Nivolumab and ipilimumab is an FDA approved combination therapy in melanoma, and is being extensively tested in NSCLC. In the CheckMate-012 study published in Lancet Oncology, four dose regimens were tested of nivolumab and ipilimumab.[9] In the two arms potentially suitable for moving forward, the treatment responses were as follows:

	Nivolumab 3 mg/kg q2 weeks + Ipilimumab 1 mg/kg q 6 weeks (n = 38)	Nivolumab 3 mg/kg q2 weeks + Ipilimumab 1 mg/kg q 12 weeks (n = 39)
Response rate	38%	47%
Median progression free survival	3.9 months	8.1 months
1 year overall survival	69%	Not calculated

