4.4 Instructions for Patients who Do Not Start Assigned Protocol Treatment

If a patient does not receive any assigned protocol treatment, baseline and follow-up data will still be collected and must be submitted through Medidata Rave and EASEE-PRO according to the schedule in the **EA5152 Forms Completion Guidelines**.

5. Treatment Plan

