5.8 Duration of Follow-up

For this protocol, all patients, including those who discontinue protocol therapy early, will be followed for radiographic response until progression, even if non-protocol therapy is initiated, and for survival for 5 years following treatment discontinuation. All patients must also be followed through completion of all protocol therapy.

6. Measurement of Effect

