7.1 Step 1: Therapeutic Parameters

Treatment should start within seven working days after registration (see Section 5)

	Screening ¹	Cycle 1 ^{1,2} (day 1)	Cycle 1 mid ² (day 15)	Cycle 2 ² (day 29)	Cycle 2 mid ² (day 43)	Cycle 3+ ² (day 57)	Post Treatment Follow Up ³
History and physical exam ⁵	X	X	X	X	X	X	X
Performance status, vital signs ⁵	X	X	X	X	X	X	
Complete blood count with differential ⁶	X		X	X	X	X	
Blood chemistry tests ⁷	X		X	X	X	X	
PT/INR and PTT	X						
Thyroid tests (TSH and reflex free T4) ⁴	X			X		X	
Electrocardiogram (ECG) ⁴	X			X		X	
Echocardiogram/MUGA ⁸	X						
Urine protein assessment ⁹	X			X		X	
Serum or Urine Pregnancy Test ¹⁰	X						
Toxicity Assessment		X	X	X	X	X	X
Tumor assessment imaging ^{11,16}	X					X ¹¹	X ³
Brain Imaging ¹²	X ¹²					X ¹²	
Nivolumab (Arms A, B, C, T)		X		X		X	
Cabozantinib (Arms B, C, T) ¹⁸		X	X	X	X	X	
Ipilimumab (Arm C)		X				X ¹⁵	
MANDATORY: Tumor Tissue ¹⁴	X						
Tobacco Use Assessment PROs ¹⁷							See Section 5.6

Cycle Length = 28 days

1. All baseline assessments must be done \leq 2 weeks before registration with the exception of imaging studies that must be done \leq 4 weeks before registration and brain imaging studies that must be done \leq 12 weeks before registration in patients without known brain metastases. Patients

with known brain metastases at baseline must have a brain MRI or head CT with contrast \leq 4 weeks prior to registration. All baseline laboratory tests can be used for Cycle 1 Day 1 treatment purposes.

2. Window for study visits and drug administration is \pm 3 days. Mid-cycle 1 and 2 visits are required for all arms. Starting with cycle 3, in-person visit by investigator is only required once per cycle.

NOTE: All hematology and chemistry assessments must be done \leq 72 hours prior to day 1 of the treatment cycle except for Cycle 1 Day 1 (see footnote 1).

3. Every 3 months until patient is 5 years from registration. Physical exam not required. If in person visit is not possible, patient should be contacted for follow up of vital status and assessment of any study-related toxicities until resolution. For patients that discontinued study therapy prior to radiographic progressive disease, tumor assessments should be performed at least every 3 months during long term follow up until progressive disease is documented.

- Rev. Add4

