Drug Ordering: Bristol-Myers Squibb and Exelixis are supplying Nivolumab, Ipilimumab, and Cabozantinib, through the Division of Cancer Treatment and Diagnosis, NCI, for this protocol. Maintenance of NCI drug accountability records is required. Drugs may be requested by the Principal Investigator (or their authorized designees) at each participating institution. Pharmaceutical Management Branch (PMB) policy requires that drug be shipped directly to the institution where the patient is to be treated. PMB does not permit the transfer of agents between institutions (unless prior approval from PMB is obtained – see general information). The CTEP-assigned protocol number must be used for ordering all CTEP-supplied investigational agents. The responsible investigator at each participating institution must be registered with CTEP, DCTD through an annual submission of FDA Form 1572 (Statement of Investigator), NCI Biosketch, Agent Shipment Form, and Financial Disclosure Form (FDF). If there are several participating investigators at one institution, CTEP-supplied investigational agents for the study should be ordered under the name of one lead investigator at that institution.

No starter supplies will be provided. Study agents must be ordered after the patient is enrolled on the assigned treatment arm. If expedited shipment is required, sites should provide an express courier account through the Online Agent Order Processing (OAOP) application.

Submit agent requests through the PMB Online Agent Order Processing (OAOP) application (<https://ctepcore.nci.nih.gov/OAOP>). Access to OAOP requires the establishment of a CTEP Identity and Access Management (IAM) account (<https://eapps-ctep.nci.nih.gov/iam>) and the maintenance of an “active” account status and a “current” password. For questions about drug orders, transfers, returns, or accountability, call or email PMB any time. Refer to the PMB’s website for specific policies and guidelines related to agent management.

NCI Supplied Agent(s) – General Information

Questions about drug orders, transfers, returns, or accountability should be addressed to the PMB by calling [contact] Monday through Friday between 8:30 AM and 4:30 PM Eastern Time or email [contact] anytime.

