9.2 Study Endpoints

Main study: Progression-free survival (PFS) is defined as the time from randomization to documented disease progression (site review of imaging) or death from any cause, whichever occurs first. Patients who have not experienced an event of interest by the time of analysis will be censored at the date they are last known to be alive and progression-free. Overall survival is defined as the time from randomization to death from any cause, and patients who are thought to be alive at the time of final analysis will be censored at the last date of contact. Best objective response will be evaluated via RECIST1.1 criteria, as described in Section [6](#) of this protocol document. Toxicity will be determined using the CTCAE criteria.

Targeted therapy sub-study: This group will be evaluated by PFS, overall survival, best objective response rate, and toxicity as above.

Exploratory Imaging Correlative Study: For RECIST1.1 (central review) and irRC PFS is defined as the time from randomization to documented disease progression or death from any cause, whichever occurs first. For iRECIST, PFS is defined as the date of the time from randomization to documented disease progression (date of the documented iUPD that is followed by subsequent iCPD) or death from any cause, whichever occurs first.

For the imaging correlates, overall survival is defined as the time from randomization to death from any cause, and patients who are thought to be alive at the time of final analysis will be censored at the last date of contact. Best objective response will be evaluated for all three criteria performed by central review as defined in Section [6](#) of this protocol document.

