9.4 Sample Size Considerations

The overall sample size for the trial is 169 patients.

Main study: The primary comparison will include all eligible and treated patients, of whom 129 will be accrued and randomized equally, for a total accrual of 43 patients per arm. After adjusting for an ineligibility rate of 10%, the total required sample size for randomization is 144 patients. Using an overall one-sided 0.10 level log rank test for each comparison, this study will have 89% power to detect a 44% reduction in the PFS hazard rate of 0.173 to 0.096 based on the estimated accrual and follow-up period. Assuming exponential survival, this corresponds to an 80% improvement in the median PFS of 4 months on nivolumab alone to 7.2 months on nivolumab plus cabozantinib or on nivolumab plus cabozantinib and

ipilimumab. The number of PFS events needed to achieve this power is 74 events under the alternative hypothesis for each of the two primary comparisons.

Targeted therapy sub-study: Up to 25 additional patients may be enrolled in Arm T. The best objective response rate and PFS will be described for this group of patients. Accrual to the study will stop when the total accrual goal for the randomized study is reached, even if 25 patients have not been enrolled to Arm T. If 25 patients enroll to Arm T before accrual to the randomized part of the study is reached, then Arm T only will be closed. With 25 patients enrolled, the maximum width of the 2-sided 90% exact binomial confidence interval for the best objective response rate will be 35%; with as few as 10 patients enrolled, it will be 56%.

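### The primary PFS comparison drops randomised patients who never start treatment, after the arm is known, and no all-randomised analysis is planned

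*Combined protocol and SAP*

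**What the plan says.** Section 9.3 sets the analysis population: "The primary and some secondary analyses will include all eligible and treated patients". Section 9.4 builds the sample size on it: "The primary comparison will include all eligible and treated patients, of whom 129 will be accrued and randomized equally". The exceptions named in 9.3 are toxicity (everyone who received drug, eligible or not) and response (a narrower set needing measurable and evaluable disease). Neither is an all-randomised set, and none is named for PFS or OS, even as a sensitivity analysis.

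The endpoint clock starts earlier than the population does. Section 9.2 says: "Progression-free survival (PFS) is defined as the time from randomization".

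Three other places matter:

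- Section 8, under drug ordering: "Study agents must be ordered after the patient is enrolled on the assigned treatment arm".
- Section 4.4: "If a patient does not receive any assigned protocol treatment, baseline and follow-up data will still be collected".
- Section 5.8 requires that "all patients, including those who discontinue protocol therapy early, will be followed for radiographic response until progression, even if non-protocol therapy is initiated".

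**The concern.** Eligibility is a baseline property. If it is judged blind to arm, excluding ineligible patients adds little bias, although the plan does not say who judges it or when. Being treated is different, because it is decided after randomisation. The three regimens are visibly different, no blinding is described, and drug is ordered only once the arm is assigned, so patient and physician know the arm before the first dose.

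There are plausible reasons for the decision to start to differ by arm. Arm A is nivolumab alone, which Section 1.1 says "is FDA approved for the treatment of squamous and non-squamous NSCLC", so a patient assigned to it may see little reason to stay on study. Arms B and C carry extra drugs and extra toxicity, which may deter frailer patients. Either pattern removes patients selectively from one arm, and the patients who remain are no longer the groups that randomisation made comparable.

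Arm A is the control in both primary comparisons, so selective loss there shifts both hazard ratios in the same direction. The stated one-sided 10% error is what randomisation delivers for the randomised groups. It is not guaranteed for a subset defined by what happened afterwards.

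**Working it through.** **1. Reproduce the design (9.4, 9.5).** Inputs: median PFS 4 and 7.2 months, one-sided alpha 0.10, 43 per arm analysed, about 15 months' accrual, total duration 25 months.

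- Hazards: ln 2/4 = 0.173 and ln 2/7.2 = 0.096. HR = 4/7.2 = 0.556.
- Schoenfeld power = Φ(½√d·|ln HR| − 1.2816). With d = 74: ½ × 8.602 × 0.588 − 1.2816 = 1.247, giving 89.4%. The plan states 89%.
- Event probability with uniform accrual A = 15 and analysis at T = 25: 1 − [exp(−λ(T−A)) − exp(−λT)]/(λA) = 0.937 (control) and 0.798 (combination).
- Expected events with 43 per arm: 43 × 1.735 = 74.6. The plan states 74.
- 129/0.9 = 143.3, rounded up to 144, or 48 per arm.

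The design is internally consistent. The 10% allowance is labelled ineligibility, and nothing separate is allowed for non-starters.

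**2. What the restricted set gives up.** 48 − 43 = 5 patients per arm, or 10 per comparison. All 48 per arm would give 48 × 1.735 = 83.3 events, so 83.3 − 74.6 = 8.7 events are lost per comparison.

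**3. Type I error under selective non-starting.** The non-start counts and prognosis here are assumptions, because the documents give neither. The simulation has no true effect, 48 per arm, the accrual and analysis times above, an unstratified log-rank test at one-sided 0.10 and 40,000 runs per case. Both arms contain k patients of the type that might decline; in the arm shown they do not start and are dropped.

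| Loss | Their hazard relative to others | k | Error, treated only |
|---|---|---|---|
| Arm A only | half | 1, 2, 3, 5, 7 | 0.116, 0.133, 0.146, 0.181, 0.220 |
| Arm A only | twice | 1, 2, 3, 5, 7 | 0.092, 0.084, 0.078, 0.064, 0.052 |
| Arm A only | same | 5 | 0.104 |
| Combination only | half | 5 | 0.048 |
| Combination only | twice | 5 | 0.154 |
| Both arms | half; twice | 5 | 0.102; 0.101 |

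In the Arm A series, testing all randomised patients gave 0.095 to 0.101 with complete follow-up. With five half-hazard patients lost from Arm A, the mean treated-only hazard ratio is 0.92 when the truth is 1.

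**4. Dependence on follow-up.** Take the same five half-hazard Arm A patients, keep them in an all-randomised test, and censor them early. At months 0, 1, 2, 3, 4 and 6 the error is 0.178, 0.166, 0.156, 0.150, 0.142 and 0.129. Keeping non-starters in the analysis set helps only as far as they are actually followed.

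**5. Power of an all-randomised test.** With 83.3 events and HR 0.556 in everyone: ½ × 9.127 × 0.588 − 1.2816 = 1.40, giving 91.9%. In simulation (20,000 runs) with 0, 2, 3 and 5 of 48 combination patients at the control hazard, power is 0.918, 0.903, 0.887 and 0.873, against 0.896 for 43 per arm. Break-even with the stated 89% is near three undiluted-to-diluted patients, that is, three combination patients who get no effect.

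**The case against.** The best defence is that this is a deliberate, pre-specified choice in a phase II trial with a one-sided 10% level, and that the sample size is built on it consistently. That is true, and it removes any suspicion of a post-hoc choice of population. It does not make the subset comparable between arms.

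The 18% case is also one-sided: five non-starters, all in Arm A, all with half the hazard. Milder assumptions move the error less. Two Arm A non-starters against one in the combination arm give 0.113 (half hazard) or 0.093 (twice). Three against one give 0.127 or 0.084. Two in Arm A alone with 0.8 times the hazard give 0.112. This objection stands as to size, but the error still leaves 10%, in a direction nobody can state in advance. Treatment should start within seven working days of registration, which narrows the window for declining but does not close it. That approval of nivolumab would lead Arm A patients to decline is conjecture.

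The loss of about 10 patients and 8.7 events per comparison is already budgeted in 9.4 as ineligibility, so it is forgone information rather than a shortfall against the stated power.

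The all-randomised test has its own weakness. Off treatment, Section 7.1 footnote 3 says "tumor assessments should be performed at least every 3 months during long term follow up until progressive disease is documented", against every 8 weeks on treatment, and it is written for patients who stopped therapy rather than those who never began. This is a real limit, and the reason to report how long each non-starter was followed.

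Finally, the concern is mainly about untreated patients, yet the change also brings ineligible patients back. Excluding them on baseline facts judged blind to arm would do little harm, but the plan does not commit to blind adjudication. Including everyone avoids the question at little cost.

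**Conclusion.** The concern holds. The primary comparison is conditioned on an event that follows randomisation in a trial with no described blinding, and no all-randomised PFS or OS analysis is described. The defect in the plan is certain, but the bias it will cause is not. With equal non-starting, or non-starters of average prognosis, the error stays near 10%. With one-sided loss of one to seven patients at half or twice the hazard, it ranges from about 5% to 22%. These figures rest on assumed counts and prognosis, exponential PFS and an unstratified test. The change is worth making because it is cheap, needs no larger sample and uses follow-up that Sections 4.4 and 5.8 already require.

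**What to change.** In Sections 9.3 and 9.4, define the primary PFS comparison on all patients randomised to Arms A, B and C, analysed as assigned, with the planned stratified log-rank test. Use the same set for OS, whose population 9.3 does not specify. Keep eligible-and-treated as a named sensitivity analysis, and leave the toxicity and response sets as they are. Restate 9.4 for 48 per arm: about 83 expected events per comparison, with power about 92% undiluted and about 87% if five of 48 combination patients get no effect. Report non-starters and ineligible patients by arm, with the length of PFS follow-up for each non-starter.

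The cost is wording, one extra analysis run and a by-arm count, with no added patients. The downsides are possible dilution of the effect, dependence on actually obtaining follow-up for non-starters, and sparser imaging off treatment.

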9.7 Randomization Scheme

Main study: Randomization to treatment will be determined using permuted blocks within strata with dynamic balancing on main ECOG-ACRIN institutions plus affiliates. The randomization will be stratified by known PD-L1 status (negative vs. positive ($\geq 1\%$) vs. unknown/not tested). It will be a 1:1:1 between arms A, B, and C.

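### Free improvement, not an error: for two-by-two comparisons of response and toxicity, Boschloo's exact test keeps the one-sided 10% level and recovers power that Fisher's test leaves unused

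*Combined protocol and SAP*

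**What the plan says.** Section 9.3 sets the test and the level for categorical outcomes: "response rates (CR+PR) and toxicity, will be compared using Fisher's exact tests with a one-sided type I error rate of 10" per cent. It states no assumed rate, target difference or power for these comparisons. The only powered comparison is PFS, for which section 9.4 says that "this study will have 89% power to detect a 44% reduction in the PFS hazard rate of 0.173 to 0.096", "Using an overall one-sided 0.10 level log rank test for each comparison".

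The numbers per arm come from two places.

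- Section 9.4 plans eligible and treated patients "randomized equally, for a total accrual of 43 patients per arm", and adds: "After adjusting for an ineligibility rate of 10%, the total required sample size for randomization is 144 patients". Section 9.7 gives the allocation: "It will be a 1:1:1 between arms A, B, and C".
- Section 9.3 uses different analysis sets for the two outcomes. Response is restricted: "analyses of response, which will include eligible and treated patients with measurable and evaluable disease". Toxicity is not: "analysis of toxicity data, which will include all patients who received study drug regardless of eligibility".

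So response has at most 43 patients per arm, and toxicity up to 48.

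Section 2.2 words both outcomes as secondary objectives, response to be estimated and toxicity to be described. Section 9.3 also plans two-sided 80% confidence intervals for all endpoints.

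**The concern.** Fisher's test conditions on the total number of events, so only a few p-values are possible at this size. The largest attainable p-value at or below 0.10 is often well below 0.10, and the test then runs at a lower level than the plan allows. The fewer the events, the wider the gap.

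The plan accepts a one-sided 10% error rate for these comparisons. A test that runs at 5%, or at 1%, gives back part of that allowance as lost power. Response is a secondary endpoint of a small randomised phase II trial, and added toxicity is the main price of the combinations, so the loss falls on comparisons that readers will look at. Another exact test avoids much of the loss without exceeding 10%.

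**Working it through.** **Inputs.** One-sided level 0.10 (9.3). Response n = 43 per arm, as an upper limit (9.3, 9.4). Toxicity n up to 144/3 = 48 per arm (9.3, 9.4, 9.7). The documents give about 3% for grade 3-5 pneumonitis and about 11% for grade 3-5 colitis with nivolumab plus ipilimumab (9.8.2), about 10% response with second-line chemotherapy (1.1), and 38% and 47% response with first-line nivolumab plus ipilimumab (1.1). All other rates, and every contrast between arms, are my assumptions.

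**The plan's own figures.** Inflation: 129/0.9 = 143.3, rounded up to 144. PFS power with 74 events: Φ(√74/2 × |ln(4/7.2)| − 1.2816) = Φ(2.528 − 1.282) = Φ(1.247) = 0.894, against the stated 89%. Both reproduce. There is no stated figure to reproduce for the Fisher comparisons.

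**Fisher's attained level.** With a events on nivolumab, b on the combination and m = a + b, the one-sided p-value is p(a,b) = Σ over k ≥ b of C(n,k)·C(n,m−k)/C(2n,m). Reject if p ≤ 0.10. The level at a common rate π is the sum of Bin(a; n,π)·Bin(b; n,π) over all rejected tables.

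**Boschloo's test.** It uses the same p(a,b) as its statistic and rejects if p ≤ c, where c is the largest cut-off whose level, maximised over π, stays at or below 0.10. Enumeration gives c = 0.1326 (maximum level 9.8%) at 43 per arm and c = 0.1354 (9.9%) at 48. Since c exceeds 0.10, it rejects every table that Fisher rejects and some more, so it cannot be less powerful.

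| Common rate | Fisher, n=43 | Boschloo, n=43 | Fisher, n=48 | Boschloo, n=48 |
|---|---|---|---|---|
| 3% | 1.1% | 4.1% | 1.4% | 4.6% |
| 5% | 2.5% | 6.1% | 2.9% | 6.6% |
| 10% | 5.0% | 8.0% | 5.5% | 8.2% |
| 11% | 5.3% | 8.1% | 5.8% | 8.4% |
| 20% | 6.1% | 8.4% | 6.3% | 8.8% |
| 30% | 6.4% | 9.6% | 7.0% | 9.9% |
| 38% | 7.4% | 9.3% | 6.5% | 9.0% |
| 47% | 8.0% | 8.2% | 6.3% | 9.2% |

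Over all rates Fisher's maximum level is 8.0% at 43 per arm and 7.1% at 48.

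**Power (one-sided).**

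| Outcome, n per arm | Contrast | Fisher | Boschloo | Gain (points) |
|---|---|---|---|---|
| Response, 43 | 10% vs 20% | 40.1% | 47.2% | 7.1 |
| Response, 43 | 10% vs 30% | 80.0% | 84.5% | 4.5 |
| Response, 43 | 20% vs 35% | 51.0% | 59.5% | 8.5 |
| Response, 43 | 20% vs 40% | 70.0% | 77.2% | 7.2 |
| Response, 43 | 30% vs 50% | 68.3% | 71.4% | 3.0 |
| Response, 43 | 20% vs 50% | 93.5% | 95.6% | 2.0 |
| Toxicity, 48 | 3% vs 12% | 49.1% | 61.9% | 12.8 |
| Toxicity, 48 | 5% vs 15% | 52.1% | 61.0% | 8.9 |
| Toxicity, 48 | 11% vs 25% | 61.1% | 67.4% | 6.3 |

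Gains are taken before rounding. Outside these toxicity contrasts, at 48 per arm, the gain is about 4 points for 3% vs 20% and about 15 for 1% vs 5%.

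**Where the gain for rare events comes from.** For 0 vs 3 events at 48 per arm, p = C(48,3)/C(96,3) = 17296/142880 = 0.121. Fisher at 0.10 does not declare this; Boschloo (c = 0.1354) does. Fisher needs 0 vs 4 (p = 0.059).

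**The case against.** The strongest reply is that nothing in the plan is wrong. Ten per cent is a nominal ceiling and Fisher's test respects it. No power is claimed for response or toxicity, the objectives speak of estimating and describing, and confidence intervals are planned as well. This stands: the point concerns efficiency, not validity. Section 9.3 nevertheless commits to formal tests at a stated level, and for those a better exact test is available at no cost.

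Three stronger readings are tempting, and the documents do not support them.

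- A reader might infer that the stated 10% is a misstatement, or that the real level is simply half of it. The attained level depends on the event rate. It reaches 7-8% at response rates of 38-47%, and Boschloo's test is itself only at 4-7% for rates of 3-5%.
- A reader might infer a fixed loss of power. The plan gives no contrasts, and the gain runs from 2 points upward according to the rates assumed. Large differences lose little.
- A reader might infer that the trial could not detect rare serious toxicity. Colitis and pneumonitis have their own rules in section 9.8.2 (5 or more, and 3 or more, of 15 patients), based on exact binomial limits. There are also twice-yearly toxicity reviews and expedited reporting. None of these uses Fisher's test.

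Two practical objections also have weight. Boschloo's test as computed here covers two-by-two tables only, while 9.3 covers categorical data generally, so the change must be limited in scope. And if many toxicity terms are tested without a multiplicity rule, a test nearer its nominal level will raise more false flags, though each test stays within the 10% that the plan already accepts.

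**Conclusion.** The point holds as an optional but worthwhile improvement. Fisher's test at a nominal one-sided 10% attains about 5-8% for response rates of 10-47% at 43 per arm, and about 1-3% for toxicities with a 3-5% rate at 43 to 48 per arm. Boschloo's test keeps the level at or below 10% and is never less powerful. Under the contrasts tabulated it gains about 2-9 points for response and about 6-13 points for toxicity.

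The levels rest on the planned numbers per arm; fewer evaluable patients would shift them somewhat. The power gains rest on assumed rates, because the plan states none. The primary PFS comparison, its sample size and the safety rules of section 9.8.2 are unaffected.

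**What to change.** In section 9.3, specify that pairwise two-by-two comparisons of each combination arm with nivolumab alone, on response (CR+PR) and on binary toxicity outcomes, use Boschloo's exact test at one-sided 10%. Keep Fisher's exact test as the named method for all other categorical tables, such as graded toxicity or three-arm tables. State the number analysed for each outcome, since response and toxicity use different sets.

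If the sponsor prefers to keep Fisher's test throughout, one sentence saying that its attained level lies below the nominal 10%, and well below it for rare events, would let readers interpret a non-significant result properly.

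The cost is a line or two of SAP text. The test is in standard software, and no patients, data or visits are added.

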2.3 Correlative Endpoints

- 2.3.1 To adjust progression free survival for each arm based on PD-L1 tumor status

Rev. Add2

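### The secondary adjusted models choose their covariates by significance testing, name no always-retained factor, and can drop the PD-L1 adjustment that the protocol promises

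*Combined protocol and SAP*

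**What the plan says.** Section 9.3 gives one modeling rule and does not limit it to exploratory work. At entry, "variables significant at the 0.10 level in the univariate setting will be chosen for inclusion in an initial full model". Then "at each step the least significant variable will be removed from the model". At the end, "Only those covariates with $p < 0.05$ will remain in any final models". The rule carries one exception, worded as follows: "unless there are factors identified by the study team as crucial to model interpretation". No factor is named as crucial, and no time is set for naming one.

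The same section gives the models their purpose. For time-to-event endpoints, "Cox proportional hazards models will be used to estimate the treatment hazard ratios". For response and toxicity, "multivariable logistic regression modeling will be used to adjust for the effect of any covariates that are associated with these categorical outcomes". The primary PFS comparison is separate: a logrank test stratified on the randomization factor, at one-sided 10%.

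Two other places promise a particular adjustment. Objective 2.3.1 reads "To adjust progression free survival for each arm based on PD-L1 tumor status". Section 11.1 says PD-L1 will be tested centrally and retrospectively with the 28-8 assay, mainly to detect imbalance between arms, and used to adjust outcomes in multivariable models. It expects a PFS hazard ratio of 0.5 for PD-L1 positive against negative, and leaves the cutpoints to the time of analysis. Sections 4.2.5 and 9.7 stratify randomization on a different PD-L1 variable: locally known status from any validated platform, in three levels (negative, positive, unknown or not tested).

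**The concern.** In a randomized comparison, covariates are best fixed before the outcomes are seen. Under the 9.3 rule the same outcome data choose the covariates and estimate the treatment effect, and the reported 80% intervals take no account of that choice. PFS, OS and response could end up with different adjusters by chance. So could the two experimental comparisons, if they are modeled separately.

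PD-L1 is the clearest case. Adjusting for it is a stated objective, and the reason given is possible imbalance. A p-value for the covariate does not show whether an imbalance needs correcting, yet under 9.3 it decides whether PD-L1 stays. The exception could rescue PD-L1, but it is discretionary and undated. The undecided cutpoint adds a further choice that can be made with results in view.

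**Working it through.** **Inputs.** Section 9.4: 74 PFS events per primary comparison, hazards 0.173 and 0.096, one-sided 0.10, 89% power. Section 9.3: thresholds 0.10 and 0.05. Section 11.1: PD-L1 hazard ratio 0.5. The documents do not give the sidedness of the selection thresholds (two-sided assumed) or PD-L1 prevalence (30% to 60% assumed).

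**Formula.** With d events and a share p of patients in one group, the test statistic has mean |ln HR| × √(d·p·(1−p)). The chance of passing critical value z is Φ(mean − z).

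**Reproducing the plan's figure.** HR = 0.096/0.173 = 0.555 and |ln HR| = 0.589. With p = 0.5, √(74 × 0.25) = 4.301, so the mean is 2.533. Φ(2.533 − 1.282) = Φ(1.252) = 0.895, which agrees with the stated 89%.

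**Chance that PD-L1 is kept**, with |ln 0.5| = 0.693, d = 74 and z = 1.960:

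| Prevalence | Mean | Kept | Missed |
|---|---|---|---|
| 30% | 0.693 × √15.54 = 2.732 | 78% | 22% |
| 40% or 60% | 0.693 × √17.76 = 2.921 | 83% | 17% |
| 50% | 0.693 × √18.5 = 2.981 | 85% | 15% |

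The earlier screen at 0.10 cannot raise these probabilities.

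**Sensitivity.**
- If p < 0.05 is read as one-sided (z = 1.645), the chance of keeping PD-L1 is Φ(2.732 − 1.645) = 0.86 to Φ(2.981 − 1.645) = 0.91, so it is missed in 9% to 14%.
- If all three arms are fitted together, with about 74 × 1.5 = 111 events, PD-L1 is kept in 92% to 95% and missed in 5% to 8%. Section 9.3 does not say whether models are pairwise or joint.

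**Instability for other factors** (d = 74, two-sided 0.05). A balanced binary factor with an assumed hazard ratio of 1.5 has mean 4.301 × 0.405 = 1.744, and Φ(1.744 − 1.960) gives 41%. For assumed hazard ratios of 1.3 and 1.8 the figures are 20% and 72%. With five irrelevant independent candidates (assumed), the chance that at least one reaches p < 0.05 is 1 − 0.95⁵ = 23%.

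**Effect on the treatment estimate.** A simulation of 3,000 trials used 86 patients, six covariates, PD-L1 at hazard ratio 0.5 and other effects assumed, with treatment kept in the model. Power was 86.4% with backward selection and 87.6% with a fixed model of PD-L1 and performance status. Coverage of the 80% interval was 77.6% and 78.8%. Unpaired Monte Carlo error on these differences is about 0.9 to 1.1 points. Simulated unadjusted power was 82.9%, below the design's 89%, so the run indicates order of magnitude only.

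**The case against.** The strongest reply is that little of consequence passes through this rule. The primary test is a logrank test already stratified on PD-L1, response and toxicity are compared by Fisher's exact test, and the OS and response objectives are to estimate. That stands. The adjusted models are supportive, and the simulated cost is about one point.

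A second reply is that section 11.1 is a specific commitment and should govern over the general rule, or that it marks PD-L1 as crucial under the exception. A sensible analyst might read it so. But 9.3 applies its rule to any final model and 11.1 claims no exemption, so the plan leaves the conflict to be settled at analysis.

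A reader might go further and infer that treatment itself can be eliminated, and that the 0.05 retention level therefore clashes with the trial's one-sided 10% test. The documents do not support this. The retention sentence speaks of covariates, the Cox models exist to estimate treatment hazard ratios, and the exception would naturally cover treatment. The plan merely omits to say that treatment is forced in. A covariate-retention threshold and a test's type I error also serve different purposes, so the difference matters only if treatment is subject to selection.

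Nor do the documents say that the exception will be applied after results are seen. They give no timing.

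**Conclusion.** The concern holds for the secondary adjusted models. Section 9.3 uses outcome-driven selection with an open-ended exception, and as written it can drop the one adjuster that objective 2.3.1 and section 11.1 require. With pairwise models at 74 events this would happen in roughly 15% to 22% of trials if the exception is not used, assuming a two-sided threshold and 30% to 60% prevalence. The figure is lower with a one-sided threshold or a joint three-arm model. The calculation is a normal approximation that ignores correlation with other covariates and assumes a usable PD-L1 result for every patient.

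The case rests on prespecification and consistency with a stated objective, not on lost efficiency. Nothing here touches the validity, power or size of the primary comparison.

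**What to change.** Amend section 9.3, before analysis, to say:
- Adjusted Cox models for PFS and OS and adjusted logistic models for response always contain treatment and the PD-L1 randomization stratum, with no removal on significance. ECOG performance status may be added; it is already collected, though eligibility limits it to 0 or 1.
- For objective 2.3.1, the model always contains treatment and the central 28-8 PD-L1 result, with the cutpoint fixed in advance in section 11.1. This variable differs from the randomization stratum, and the text should say which model uses which.
- Backward selection is limited to exploratory prognostic models, labeled as such.

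This changes wording only and needs no new data. The cost is one or two degrees of freedom per model (one for a binary central result, two for the three-level stratum), plus one if performance status is added, spent on covariates that may prove weak.
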